7.9.3.1 EQ-5D-5L

To characterize the EQ-5D-5L of the preferred aDBS mode as compared to cDBS Baseline.

Endpoint definition

The European Quality of Life – 5 Dimensions, version 5L (EQ-5D-5L) will be collected at visit 2 and visit 3.

Analysis methods

The European Quality of Life – 5 Dimensions, version 5L (EQ-5D-5L) will assess generic health status by five dimensions (mobility, self-care, usual activities, pain/discomfort, and anxiety/depression) on 5 levels of severity (no problems, slight problems, moderate problems, severe problems, extreme problems) and by the visual analogue scale (VAS). The responses to the five EQ-5D dimensions (i.e. an EQ-5D health state or profile) will be converted into an index value using the Japanese value set. The EQ-5D dimensions will be summarized as categorical measures and the index value and visual analog scale (VAS) will be summarized as continuous measures for both cDBS and aDBS and by aDBS preferred mode.

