9.6 Baseline

The baseline visit must occur within 30days after subject enrollment.

The PI/ Sub investigator will screen potential subjects by reviewing the study's inclusion/exclusion

criteria.

Enrolled subjects who do not meet all inclusion criteria or who meet any exclusion criteria will be discontinued from the study. No further study-related procedures will be completed, and subjects will be followed according to the site's standard procedures.

The PI/ Sub investigator will ensure the INS device time matches that of the clinician programmer tablet (network enabled). If the INS time does not match the network time, the INS time should be updated.

The following data will be collected at Baseline:

- Demographics (age, sex)*
- Medical & surgical history*
- PD history*
- Signal test (If implemented)
- Patient preference questionnaire. *
- Concomitant medications (non-PD)
- PD medication (When performing a signal test with Off PD medication, PD medication and does given at visit. Time of last dose of PD medications taken prior to the visit)
- Device identification information, including historical DBS implant information*
- Programming session upload, with device interrogation and BrainSense data included in the JSON session data report (If Signal test was implemented)
- Pre-op/post-op Magnetic Resonance Image (MRI) images and Computed Tomography (CT) images of Percept PC implant *
- AE and device deficiency assessment (As they occur)
- Protocol Deviations (As they occur)

*It is stated in the IC and consent is obtained from the subjects that these data collected prior to Early Adapter Part II are used for this study.

If both aDBS modes (single and dual threshold) are acceptable, a preference questionnaire is used to determine the preferred aDBS mode (single or dual threshold) for the subject. If the subject answers "Do not know" or "No preference" to the question "Which adaptive DBS mode do you prefer?", the PI/

Sub investigator determines the aDBS (preferred mode) which is suitable for the treatment of the patient.

The PI/ Sub investigator selects dual threshold mode from the BrainSense™ setup to set the LFP threshold if the subject's LFP threshold has not been set. The subjects who are on aDBS mode will leave the visit on cDBS settings (including BrainSense settings) in order to wash out aDBS for 7 days or more.

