9.8.1. Period A initiation /Visit1

Same as Randomization day.

The PI/ Sub investigator should confirm the subject is in cDBS.

The following data will be collected:

- Concomitant medications (non-PD)
- PD medications
- Programming session upload, with device interrogation and BrainSense data included in the JSON session data report
- PDQ-39 (subject's assessment of cDBS or aDBS washout period)
- EQ-5D-5L
- MDS-UPDRS II ("best" conditions)
- MDS-UPDRS II ("worst" conditions)
- MDS-UPDRS III (On stim (cDBS)/On med) – trained rater
- MDS-UPDRS IV – trained rater
- UDysRS (subject's assessment of cDBS or aDBS washout period)
- Upload data collected from Apple Watch, including movement and sleep data (Operation confirmation)
- AE and device deficiency assessment (As they occur)
- Protocol Deviations (As they occur)

At the end of the visit, the PI/Sub investigator should program the subject to the assigned DBS mode for Period A. Start the program for Period A, and return the subject home.

Subjects will participate in a data collection of movement, sleep data and dosing cycle of PD medications with Apple Watch and iPhone. The subject will be given an Apple Watch and linked iPhone and instructed on its use. Upon receipt, the subjects should put on and activate the Apple Watch. Data collection will start immediately and will continue as long as the subject is wearing the watch and the watch is charged. After the recording, the subject will upload the data collected from Apple Watch via iPhone to the database specified by Rune Labs, Inc. Subjects will also record their PD medications in an iPhone application (STRIVE App, Rune Labs) every 14 days during Period A and Period B in aDBS treatment phase. An Apple Watch calendar will be set up to get notifications from Apple Watch for medication log. Subjects will receive further guidance on the daily charging schedule of the Apple Watch and data upload through the iPhone application (STRIVE App, Rune Labs, Inc.). Detailed procedures for the Apple Watch/iPhone data collection are outlined in the Rune Labs Study Manual. In principle, the data collected from an iPhone will be used for Data of PD medication cycle, but if the data is missing, the data recorded in a medication diary etc. can substitute by reporting in CRFs.

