12.7.1. Additional Objective #1

To characterize EQ-5D-5L by aDBS and cDBS, and by aDBS preferred mode. The EQ-5D will assess generic health status by five dimensions (mobility, self-care, usual activities, pain/discomfort, and anxiety/depression) and the visual analogue scale (VAS). This endpoint will be described by summary statistics. The EQ-5D dimensions will be summarized as categorical measures using frequency counts and percentages and the index value and visual analog scale (VAS) will be summarized as continuous measures and summarized using standard descriptive statistics including the mean, standard deviation, median and range or interquartile range. The above summary statistics will be reported by aDBS and cDBS and within the aDBS by preferred mode single and dual threshold.

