7.1 Study Subjects

7.1.1 Disposition of Subjects

Subject disposition will be illustrated according to the extension of CONSORT Statement¹ for crossover trial and attrition will be identified and summarized. The number of subjects enrolled, randomized, and who underwent cDBS and aDBS adjustment phases will be summarized.

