7.9.3.2 PDQ-39

To characterize the Parkinson's Disease Questionnaire (PDQ)-39 Summary Index (SI) and subscores: mobility, activities of daily living, emotional well-being, stigma, social support, cognition, communication, bodily discomfort.

Endpoint definition

The Parkinson's Disease Questionnaire is a self-completion Patient Reported Outcome (PRO) designed to address aspects of functioning and well-being for those affected by Parkinson's disease. The PDQ-39 will be collected at cDBS and at each aDBS adjustment phase.

Analysis methods

The PDQ-39 is a 39 questions assessment with 8 discrete scales:

- mobility (10 items, questions number 1 to 10)
- activities of daily living (6 items, questions number 11 to 16)
- emotional well-being (6 items, questions number 17 to 22)
- stigma (4 items, questions number 23 to 26)
- social support (3 items, questions number 27 to 29)
- cognitions (4 items, questions number 30 to 33)
- communication (3 items, questions number 34 to 36)
- bodily discomfort (3 items, questions number 37 to 39)

Patients are asked to think about their health and general well-being and to consider how often in the last month they have experienced certain events (e.g. difficulty walking 100 yards). Each patient is asked to indicate the frequency of each event using a rate on a 5 points scale (ranging from 0 to 4 reflecting the subject's rating; never/occasionally/sometimes/often/always or cannot do at all), higher scores indicating higher frequency of each event. Each domain is calculated as a scale from 0 to 100, where 0 represents no problem at all and 100 represents the maximum level of problem.

The formula for scoring each domain is:

$$\frac{\text{sum of scores of each question in domain}}{4 \times \text{number of questions in domain}} \times 100$$

The PDQ-39-SI is scored as:

$$\frac{\text{sum of all domain scores}}{8}$$

The PDQ-39 Summary Index (SI) and the 8 subscales will be summarized for this outcome² by summary statistics as mean, standard deviations and 95% confidence intervals (CIs). The PDQ-39 Summary Index (SI) and sub-scores will be summarized for both cDBS and aDBS and by aDBS preferred mode. If the response to a question is missing, no scale score is calculated for that individual for that domain. This precludes the calculation of the PDQ-39 summary index score.

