7.9.3.3 UDysRS

To characterize the Unified Dyskinesia Rating Scale (UDysRS).

Endpoint definition

The Unified Dyskinesia Rating Scale (UDysRS) is developed to evaluate involuntary movements often associated with treated Parkinson's disease. The UDysRS will be collected at cDBS and at each aDBS adjustment phase.

Analysis methods

The Unified Dyskinesia Rating Scale (UDysRS) has two primary sections:

- Historical (from question 1 to 15):
 - Part 1 (On-Dyskinesia)
 - Part 2 (Off-Dystonia)
- Objective (from question 16 to 26):
 - Part 3 (Impairment)
 - Part 4 (Disability)

Each sub-score will be calculated as the sum of scores within the section (see Figure 7-1). The total UDysRS score will be calculated as the sum of the Historical and Objective sub-score. Results will be presented overall and separately by sub-score by summary statistics as mean, standard deviations and 95% confidence intervals (CIs) and summarized for both cDBS and aDBS and by aDBS preferred mode

Figure 7-1. UDysRS score summary

Historical	Score	Objective	Score
1. Time dyskinesia		16. Face	
2. Speech		17. Neck	
3. Chewing/Swallowing		18. Right Hand/arm/shoulder	
4. Eating tasks		19. Left Hand/arm/shoulder	
5. Dressing		20. Trunk	
6. Hygiene		21. Right foot/leg/hip	
7. Handwriting		22. Left foot/leg/hip	
8. Doing hobbies/activities		23. Communication	
9. Walking/balance		24. Drinking	
10. Public/social		25. Dressing	
11. Exciting situations		26. Ambulation	
12. Time Off dystonia			
13. Dystonia effects on activities (not pain)			
14. Effect of Pain from dystonia			
15. Dystonia pain severity			
Historical sub-score (sum)		Objective sub-score (sum)	
Total UDysRS score (Historical + Objective):			

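### SAP 7.9.3 does not fix which visits give the aDBS and cDBS clinical scores, and 7.9.3.1 names a baseline comparator that contradicts its own visits and the randomised crossover

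*SAP*

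**What the plan says.** **EQ-5D-5L (SAP 7.9.3.1).** The aim is "To characterize the EQ-5D-5L of the preferred aDBS mode as compared to cDBS Baseline". The endpoint definition directly below it says that the scale "will be collected at visit 2 and visit 3". The protocol's version of the objective (12.7.1) mentions no baseline: "To characterize EQ-5D-5L by aDBS and cDBS, and by aDBS preferred mode".

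**PDQ-39 and UDysRS (SAP 7.9.3.2 and 7.9.3.3).** "The PDQ-39 will be collected at cDBS and at each aDBS adjustment phase", and likewise "The UDysRS will be collected at cDBS and at each aDBS adjustment phase". Neither section gives visit numbers. The same phase name appears under disposition in SAP 7.1.1: "The number of subjects enrolled, randomized, and who underwent cDBS and aDBS adjustment phases will be summarized". SAP Appendix A speaks of an adjustment visit.

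**The general rule (SAP 7.9.3).** Each additional objective is to be reported as a cDBS mean, an aDBS mean and the aDBS-to-cDBS difference with a 95% CI. Source visits are not stated. Protocol 12.7 does not state them either.

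**What the trial collects.** In the visit schedules of both documents, all three scales are taken at Visits 1 to 6 and none at the Baseline visit. Protocol sections 9.8 and 9.9 describe a treatment phase with Periods A and B, then a follow-up phase. There is no adjustment phase.

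**The concern.** In a two-period crossover every subject supplies a randomised, subject-blinded cDBS score at Visit 2 or Visit 3. That score is the natural comparator for the aDBS score from the other period. A programmer who takes the EQ-5D-5L aim literally would look for a pre-treatment cDBS value and find only Visit 1. The reported difference would then be a before-after change, open to time trend, expectation and familiarity with the questionnaire.

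For PDQ-39 and UDysRS the text names no baseline comparator, but it does not identify the right visits either. Visit 1 is a cDBS visit and Visits 4–6 are aDBS visits, so nothing in 7.9.3 keeps them out of the two means. Visits 4–6 follow unblinding and include only subjects who stay on aDBS.

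These scales are the patient-facing evidence beside an energy-based primary endpoint. SAP 7.11 requires an amendment only when a principal feature changes, so the choice of visits could be settled late and merely described in the report.

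**Working it through.** The plan gives no figure on this point to reproduce. The check sets the visits side by side, then asks what each possible contrast estimates.

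**1. Status of each visit (protocol 9.6 to 9.9)**

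| Visit | Mode | Subject blinded? | Randomised? |
|---|---|---|---|
| Visit 1 | cDBS for all; assigned mode programmed only at the end of the visit | No; subjects are told at baseline about staying in cDBS mode | No |
| Visits 2 and 3 | Assigned mode, one of each per subject | Yes | Yes |
| Visits 4–6 | aDBS, in those who continue on it | No; blind broken after Visit 3 | No |

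**2. Expected difference when there is no treatment effect**

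Let *a* and *b* be the mean shifts in score, relative to Visit 1, at the ends of Periods A and B. Assume equal sequence sizes and no carryover.

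- Visits 2 and 3: the aDBS-first sequence gives *a* − *b* and the cDBS-first sequence gives *b* − *a*. The average is **0** for any *a* and *b*.
- aDBS period against Visit 1: the sequences give *a* and *b*. The average is **(*a* + *b*)/2**.
- aDBS period against a cDBS mean that averages Visit 1 with the cDBS period: the sequences give *a* − *b*/2 and *b* − *a*/2. The average is **(*a* + *b*)/4**.

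Example with *a* = 0.2 and *b* = 0.4: the three contrasts are 0, 0.30 and 0.15.

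**3. How often the 95% CI would exclude zero**

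The documents give no size for *a* or *b*, so the range is an assumption. Take n = 20, the planned number completing the treatment phase, and express the mean shift against Visit 1 in SDs of the paired difference. The probability comes from the noncentral t distribution with 19 degrees of freedom and noncentrality shift × √20.

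| Assumed mean shift (SD) | CI excludes 0, contrast against Visit 1 |
|---|---|
| 0 | 5.0% |
| 0.2 | 13.6% |
| 0.3 | 24.7% |
| 0.5 | 56.5% |

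**4. Recall period of the PDQ-39**

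- Visits 2 and 3: protocol 9.8.2 and 9.8.3 ask about the preceding 30 days on the assigned mode. The shortest period is 45 − 7 = 38 days, so 30 days fit wholly inside it.
- Visit 1, read by the protocol: "PDQ-39 (subject's assessment of cDBS or aDBS washout period". Subjects who arrive on aDBS are switched to cDBS at baseline "in order to wash out aDBS for 7 days or more", so the window may be as short as 7 days.
- Visit 1, read by SAP 7.9.3.2, which describes the PDQ-39 as covering the preceding month: with the minimum washout, 30 − 7 = 23 of 30 days (77%) were on aDBS. With a 30-day washout, still allowed by the limit of 30 days from baseline to randomisation, it is 0 of 30.

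On the first reading the recall length can differ from that at Visits 2 and 3. On the second, the Visit 1 score may be only partly a cDBS score.

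**The case against.** The strongest reply is that the rest of the text already points to the randomised periods. SAP 7.9.3.1 itself names Visits 2 and 3 and summarises by cDBS and aDBS. SAP 7.2 requires summaries by randomisation group and period. Protocol 9.8.2 and 9.8.3 tie PDQ-39 and UDysRS at those visits to the assigned mode. Adjustment phase can be read as loose wording for the treatment periods, since SAP 7.1.1 lists it after randomisation.

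Most of this stands, and it rules out three stronger readings that a reader might infer.

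- *The SAP has adopted an unblinded before-after analysis of the clinical scales.* The documents do not support this. For EQ-5D-5L there is an internal contradiction, not a settled plan. For PDQ-39 and UDysRS no baseline comparator is named. aDBS scores at Visits 2 and 3 are subject-blinded.
- *Visit 1 PDQ-39 and UDysRS mostly describe aDBS.* The 77% is a worst case. It sets aside the protocol's instruction to assess the cDBS or washout period and assumes the minimum washout, and the share of subjects arriving on aDBS is not stated. It does not carry over to UDysRS items 16–26, the Objective section.
- *The biases could not be disentangled later.* They could. All three scales are collected at Visits 2 and 3, so the randomised contrast can always be computed.

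The reply does not supply the missing definition. Summaries by group and period do not say which scores form the aDBS-to-cDBS difference, and the baseline comparator remains in the EQ-5D-5L aim.

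**Conclusion.** The point holds as an inconsistency and an omission. SAP 7.9.3.1 names a comparator that conflicts with its own visits and with the design. SAP 7.9.3.2 and 7.9.3.3 refer to phases that this trial does not have. SAP 7.9.3 leaves open which of Visits 1 to 6 supply the means, the difference and its CI.

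If the stated EQ-5D-5L comparator were followed, the difference would absorb (*a* + *b*)/2 of any time or expectation shift, which the Visit 2 and 3 contrast balances by design. The 14% to 57% range rests on assumed shifts of 0.2 to 0.5 SD with 20 subjects. It illustrates the exposure and is not a prediction.

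The reach is limited. These are additional objectives without hypothesis tests, although the SAP attaches a 95% CI to each difference. The primary and secondary analyses are not affected.

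**What to change.** Amend the SAP wording:

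- **7.9.3.1:** replace the baseline comparator with *the randomised cDBS period (Visit 2 or Visit 3 according to sequence)*.
- **7.9.3.2 and 7.9.3.3:** define the compared values as the Visit 2 and Visit 3 scores by assigned mode.
- **7.9.3:** state that the aDBS mean, the cDBS mean, their difference and its 95% CI use Visits 2 and 3 within subject. Report Visit 1 and Visits 4–6 separately as descriptive summaries.
- **7.1.1 and Appendix A:** replace the adjustment phase and adjustment visit terms with this trial's own period and visit names.

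The cost is a text amendment. No new data, visits or subjects are needed.

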7.9.3.2 PDQ-39

To characterize the Parkinson's Disease Questionnaire (PDQ)-39 Summary Index (SI) and subscores: mobility, activities of daily living, emotional well-being, stigma, social support, cognition, communication, bodily discomfort.

Endpoint definition

The Parkinson's Disease Questionnaire is a self-completion Patient Reported Outcome (PRO) designed to address aspects of functioning and well-being for those affected by Parkinson's disease. The PDQ-39 will be collected at cDBS and at each aDBS adjustment phase.

Analysis methods

The PDQ-39 is a 39 questions assessment with 8 discrete scales:

- mobility (10 items, questions number 1 to 10)
- activities of daily living (6 items, questions number 11 to 16)
- emotional well-being (6 items, questions number 17 to 22)
- stigma (4 items, questions number 23 to 26)
- social support (3 items, questions number 27 to 29)
- cognitions (4 items, questions number 30 to 33)
- communication (3 items, questions number 34 to 36)
- bodily discomfort (3 items, questions number 37 to 39)

Patients are asked to think about their health and general well-being and to consider how often in the last month they have experienced certain events (e.g. difficulty walking 100 yards). Each patient is asked to indicate the frequency of each event using a rate on a 5 points scale (ranging from 0 to 4 reflecting the subject's rating; never/occasionally/sometimes/often/always or cannot do at all), higher scores indicating higher frequency of each event. Each domain is calculated as a scale from 0 to 100, where 0 represents no problem at all and 100 represents the maximum level of problem.

The formula for scoring each domain is:

$$\frac{\text{sum of scores of each question in domain}}{4 \times \text{number of questions in domain}} \times 100$$

The PDQ-39-SI is scored as:

$$\frac{\text{sum of all domain scores}}{8}$$

The PDQ-39 Summary Index (SI) and the 8 subscales will be summarized for this outcome² by summary statistics as mean, standard deviations and 95% confidence intervals (CIs). The PDQ-39 Summary Index (SI) and sub-scores will be summarized for both cDBS and aDBS and by aDBS preferred mode. If the response to a question is missing, no scale score is calculated for that individual for that domain. This precludes the calculation of the PDQ-39 summary index score.

7.9.3.3 UDysRS

To characterize the Unified Dyskinesia Rating Scale (UDysRS).

Endpoint definition

The Unified Dyskinesia Rating Scale (UDysRS) is developed to evaluate involuntary movements often associated with treated Parkinson's disease. The UDysRS will be collected at cDBS and at each aDBS adjustment phase.

Analysis methods

The Unified Dyskinesia Rating Scale (UDysRS) has two primary sections:

- Historical (from question 1 to 15):
 - Part 1 (On-Dyskinesia)
 - Part 2 (Off-Dystonia)
- Objective (from question 16 to 26):
 - Part 3 (Impairment)
 - Part 4 (Disability)

Each sub-score will be calculated as the sum of scores within the section (see Figure 7-1). The total UDysRS score will be calculated as the sum of the Historical and Objective sub-score. Results will be presented overall and separately by sub-score by summary statistics as mean, standard deviations and 95% confidence intervals (CIs) and summarized for both cDBS and aDBS and by aDBS preferred mode

Figure 7-1. UDysRS score summary

Historical	Score	Objective	Score
1. Time dyskinesia		16. Face	
2. Speech		17. Neck	
3. Chewing/Swallowing		18. Right Hand/arm/shoulder	
4. Eating tasks		19. Left Hand/arm/shoulder	
5. Dressing		20. Trunk	
6. Hygiene		21. Right foot/leg/hip	
7. Handwriting		22. Left foot/leg/hip	
8. Doing hobbies/activities		23. Communication	
9. Walking/balance		24. Drinking	
10. Public/social		25. Dressing	
11. Exciting situations		26. Ambulation	
12. Time Off dystonia			
13. Dystonia effects on activities (not pain)			
14. Effect of Pain from dystonia			
15. Dystonia pain severity			
Historical sub-score (sum)		Objective sub-score (sum)	
Total UDysRS score (Historical + Objective):			

7.9.3.4 MDS-UPDRS

To characterize the Movement Disorder Society-Sponsored Revision of Unified Parkinson's Disease Rating Scale (MDS-UPDRS).

Endpoint definition

The MDS-UPDRS part II (best and worst), part III and part IV will be used to assess motor PD symptoms.

Analysis methods

The MDS-UPDRS is a comprehensive assessment of both motor and non-motor PD symptoms. The assessment has four parts:

- Part I (non-motor experiences of daily living) not included in this study
- Part II Best (motor experiences of daily living) condition and Part II Worst (motor experiences of daily living) condition
- Part III (motor examination)
- Part IV (motor complications)

Each question is scored from 0 to 4 reflecting the subject's usual level of function; Normal, Slight, Mild, Moderate and Severe. Each part can be reported as sub-scores.

The MDS-UPDRS II (best and worst) is a 13 questions assessment of experiences of daily living. Each parkinsonian sign or symptom from 2.1 to 2.13 is rated on a 5 points scale (ranging from 0 to 4 reflecting the subject's usual level of function; Normal, Slight, Mild, Moderate and Severe), with higher scores indicating more severe impairment. The maximum total MDS-UPDRS II score is 52, indicating the worst

possible experiences of daily living. These items will be summarized by summary statistics for both cDBS and aDBS and by aDBS preferred mode.

The MDS-UPDRS III is a 18 questions assessment of motor PD symptoms. Each parkinsonian sign or symptom from 3.1 to 3.18 is rated on a 5 points scale (ranging from 0 to 4 reflecting the subject's usual level of function; Normal, Slight, Mild, Moderate and Severe), with higher scores indicating more severe impairment. The maximum total MDS-UPDRS III score is 72, indicating the worst possible motor disability from PD. These items will be summarized by summary statistics for both cDBS and aDBS and by aDBS preferred mode.

The MDS-UPDRS IV is a 6 questions assessment of motor PD complication. Each parkinsonian sign or symptom from 4.1 to 4.6 is rated on a 5 points scale (ranging from 0 to 4 reflecting the subject's usual level of function; Normal, Slight, Mild, Moderate and Severe), with higher scores indicating more severe impairment. The maximum total MDS-UPDRS III score is 24, indicating the worst possible motor complication. These items will be summarized by summary statistics for both cDBS and aDBS and by aDBS preferred mode.

